9.6 Analyses

9.6.1 Primary Analysis

Lipid measurements from week 2 and week 14 will be used for analyses of the primary endpoints. We will use intention-to-treat analyses for evaluation of the primary endpoint and logistic regressions to compare percent change in LDL-c from week 2 to week 14 for the high-intensity statin group versus the lower intensity statin group.

The primary analysis will evaluate percent changes in LDL-c at week 14 compared with week 2 (following wash-in with pravastatin 40mg daily) for patients randomized to a high intensity versus lower intensity strategy. Two-sample t-tests will be performed using STATA version 14 (Stata Statistical Software: Release 14; College Station, TX: StataCorp LP).

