6.0 CLINICAL AND LABORATORY EVALUATIONS

6.1 Schedule of Events

	SCREEN- ING	WEEK 0 ^a	WEEK 2 ^a	WEEK 6 ^a	WEEK 10	Week 14/ or discontinuation
Informed Consent	X	X				
Medical and Medication History (including cardiovascular risk; HIV RNA and CD4, lipids)	X					
Complete Physical Exam	X					
Targeted Physical Exam		X	X	X	X	X
Height , Weight	X				X	
Vital Signs	X	X	X	X	X	X
Chemistry Panel, Liver Function Tests	X	X	X	X	X	X
Creatine Kinase	X	X	X	X	X	X
Fasting Lipid Panel	X	X	X	X	X	X
Pregnancy Test	X	X				X
Hematology, Hemoglobin A1c		X				X
Stored Plasma/Serum/PBMCs		X	X			X
Pharmacokinetics/dynamics			X	X		X
Randomization			X			
Dispensing of Study Drug		X	X	X	(X)*	
Adherence Assessment			X	X	X	X
Concomitant Medication Review	X	X	X	X	X	X
AE Determination		X	X	X	X	X
Phone Call					(X)*	
Statin Intolerance Survey			X	X	X	X

*(X) if on escalated rosuvastatin dose (40mg daily)

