6.2.4 Discontinuation Evaluations

Evaluations for Registered Subjects Who Do Not Start Study Treatment

Subjects who do not begin study treatment should have screening and entry forms completed and entered in the database. Beyond the entry visit, no further evaluations are required. These subjects will be replaced.

Premature Treatment Discontinuation Evaluations

Subjects who discontinue the study medications before the end of the study (Week 14) should have the Premature Treatment Discontinuation evaluations done within 7 days after stopping study drugs. They will be encouraged to continue to attend all study visits and receive study evaluations as per section 6.1 through Week 14.

Premature Study Discontinuation Evaluations

All subjects who prematurely discontinue participation in the study should have the Premature Study Discontinuation evaluations done.

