6.3.5 Laboratory Evaluations

Sites must refer to the DAIDS Table for Grading the Severity of Adult and Pediatric Adverse Events (DAIDS AE Grading Table), Version 2.0, November 2014, which can be found at <http://rsc.tech-res.com/safetyandpharmacovigilance/gradingtables.aspx>.

Record all protocol-required laboratory values, regardless of grade, obtained at screening and entry on the CRFs.

After entry, record all laboratory values Grade ≥ 2 . Record all lipid values (Total, HDL, and LDL cholesterol, triglycerides) regardless of grade on the CRF. All laboratory values that lead to a change in study treatment, and all serum creatinine and liver function tests (AST, ALT, alkaline phosphatase, total bilirubin) regardless of grade, must be recorded.

Hematology

Hemoglobin, hematocrit, white blood cell count (WBC), with differential, absolute neutrophil count (ANC), and platelet count.

Liver Function Tests

AST (SGOT), ALT (SGPT), alkaline phosphatase, total and direct bilirubin

Blood Chemistries

sodium, potassium, chloride, bicarbonate, random glucose, BUN, creatinine, aspartate aminotransferase (AST/SGOT), alanine aminotransferase (ALT/SGPT), alkaline phosphatase, total bilirubin, direct bilirubin, total protein, and albumin.

Fasting Lipids

Total, HDL, and LDL cholesterol, triglycerides.

If triglycerides are >400 at screening and/or high enough that LDL can't be calculated, then come back for direct LDL. Subsequent LDL should be direct in those patients.

Subjects should be instructed to fast for 8 hours prior to this test. Fasting is defined as no food or drink, except for sips of water with medications. If the subject has not been fasting, the visit must be rescheduled. Record the non-fasting status on the CRF.

Pregnancy Test

All women with reproductive potential must have a negative serum or urine beta-human chorionic gonadotropin (β -HCG) pregnancy test result at screening and within 48 hours prior to initiating protocol-specified medications and any time thereafter when pregnancy is suspected. (The urine test must have a sensitivity ≤ 50 mIU/mL).

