9.2 Endpoints

9.2.1 Primary Endpoints:

Efficacy: The primary efficacy endpoint is mean percent change in fasting LDL-c (mg/dl) from week 2 (end of run-in period) to week 14

- The mean percent change in fasting LDL-c from week 2 to week 14 will be compared for the high dose group (rosuvastatin 20mg daily uptitrated to 40mg daily) and the moderate dose group (pravastatin 40mg daily).

Safety:

- All treatment-emergent adverse events, including but not limited to:
 - Incidence of adverse event-related study drug discontinuation (following initial 2 week wash-in) or hospitalizations
 - Grade 3 or greater adverse events;
 - Study drug-related symptoms
 - CK elevation > 3x upper limit of normal;
 - AST or ALT elevation >3x upper limit of normal;

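### The primary analysis is an unadjusted t-test on weeks 2 and 14 only: it loses randomised patients without a week-14 LDL-c and ignores week-2 adjustment and the week 6 and 10 values

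*Combined protocol and SAP*

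**What the plan says.** Section 9.2.1 defines the endpoint: "The primary efficacy endpoint is mean percent change in fasting LDL-c (mg/dl) from week 2 (end of run-in period) to week 14". Section 9.6.1 sets the data and the method. On data: "Lipid measurements from week 2 and week 14 will be used for analyses of the primary endpoints". On method it gives two statements: "We will use intention-to-treat analyses for evaluation of the primary endpoint and logistic regressions to compare percent change in LDL-c", and then "Two-sample t-tests will be performed using STATA version 14". No covariate is named, although section 9.3 stratifies randomisation by ART booster use and known CHD (section 4.3.2 lists booster use only). Section 9 does not define the intention-to-treat set, and gives no rule for a missing week-14 value and no missing-data sensitivity analysis.

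The schedule in section 6.1 marks the row "Fasting Lipid Panel" at screening and weeks 0, 2, 6 and 10, and in a last column headed "Week 14/ or discontinuation". Section 6.3.5 puts every result in the database: "Record all lipid values (Total, HDL, and LDL cholesterol, triglycerides) regardless of grade on the CRF".

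For patients who stop drug early, section 6.2.4 asks for an evaluation within 7 days and adds: "They will be encouraged to continue to attend all study visits". Sections 7.1.2, 7.1.3, 7.1.4 and 7.2 say such patients are followed off treatment to the study termination visit. Section 9.5 keeps those stopped by the medical safety officer in follow-up and in the intention-to-treat analyses. Section 8.2 allows withdrawal from the study altogether.

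**The concern.** The label and the method do not match. An intention-to-treat comparison covers everyone randomised, whereas a t-test on week 2 to week 14 change covers only those with both values. If missing week 14 is related to how LDL-c would have turned out, the comparison is biased, and the size and direction depend on which arm loses which patients.

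The method also leaves information unused. Week-2 LDL-c is normally the strongest predictor of week-14 LDL-c, yet it enters only as the denominator of the percent change. Weeks 6 and 10 would inform the week-14 estimate for patients who drop out late. In a trial of 30 to 50 patients, both matter.

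Finally, the plan names two methods for one endpoint, one of them for binary outcomes. In an open-label trial the method, and the handling of missing and early-exit values, should be fixed before the data are examined.

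**Working it through.** **1. The plan's own sample size.** Section 9.4 gives a difference of 25 mg/dl, SD 20, power 0.80 and two-sided alpha 0.05.

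n per arm = 2 × (1.960 + 0.842)² × 20² / 25² = 10.05, rounded up to 11. This matches the plan.

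The enrolment goal is 22 + 8 = 30, so the sizing treats the 8 expected drug discontinuations as lost, while section 9.5 keeps those stopped for safety in the analysis. Noncentral-t power if 8 patients (4 per arm) lack week 14:

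| Enrolled | Per arm with week 14 | Power | Power if complete |
|---|---|---|---|
| 30 | 11 | 79.6% | 91.0% |
| 40 | 16 | 92.8% | 97.1% |
| 50 | 21 | 97.7% | 99.1% |

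If all 8 are in one arm, power is 73.8% at 30 enrolled and 91.2% at 40. These figures are on the mg/dl scale; the plan gives no SD for percent change.

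**2. Precision.** The documents give no within-patient correlation. Assume equal variance σ² at each visit and a correlation of 0.5 to 0.7, either the same between all visits (exchangeable) or per 4-week step (autoregressive, so week 2 to week 14 is the cube). With r the week 2 to week 14 correlation and complete data, per-patient variances are:

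- change score: 2σ²(1 − r)
- baseline-adjusted (ANCOVA): σ²(1 − r²)
- ratio of ANCOVA to change score: (1 + r)/2

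| Structure | r | Ratio | Reduction |
|---|---|---|---|
| Exchangeable 0.7 | 0.70 | 0.850 | 15% |
| Exchangeable 0.5 | 0.50 | 0.750 | 25% |
| Autoregressive 0.7 | 0.343 | 0.672 | 33% |
| Autoregressive 0.5 | 0.125 | 0.563 | 44% |

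Baseline adjustment alone therefore gives 15-44%. With complete data, weeks 6 and 10 add nothing to the week-14 contrast. When 10-27% lack week 14 (27% is 8/30) but have weeks 6 and 10, the information-matrix variance of the repeated-measures model is about 2% (exchangeable 0.5, 10% missing) to 11% (autoregressive 0.7, 27% missing) below ANCOVA in completers. The full range against the change-score t-test is 15-47%.

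**3. Bias, as an illustration.** Section 9.4 expects LDL-c of 75 on pravastatin, 50 on rosuvastatin and about 105 at entry. Take 105 as the off-drug level. From 75 at week 2, the on-drug change is −33.3% on rosuvastatin and 0% on pravastatin, and the off-drug change is +40%. Assume 20 per arm, and that half of the discontinuers miss week 14.

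Four discontinuers on rosuvastatin, none on pravastatin:
- all 20: (−33.3 × 16 + 40 × 4)/20 = −18.6%
- those with week 14: (−33.3 × 16 + 40 × 2)/18 = −25.2%
- too favourable by 6.5 points

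Four discontinuers in each arm:
- pravastatin, all 20: (0 × 16 + 40 × 4)/20 = +8.0%; with week 14: (0 × 16 + 40 × 2)/18 = +4.4%
- arm contrast, all: −18.6 − 8.0 = −26.6; with week 14: −25.2 − 4.4 = −29.6
- too favourable by 3.0 points

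**4. Bias and precision by simulation.** This used 4,000 replicates per scenario, SD 20, autoregressive correlation 0.6 or 0.8, a true difference of −25 mg/dl and 4 patients per arm without week 14. When rosuvastatin patients with poor week-10 values were likelier to be missing, completers gave −26.9 and −26.3 at 30 enrolled and −26.6 and −26.0 at 40, about 1 to 2 mg/dl too favourable. An analysis using weeks 6 and 10 gave −25.0 to −25.2. With missingness at random within arm at 30 enrolled, the standard error was 10.6 / 8.4 for completers, 9.8 / 7.8 using weeks 6 and 10, and 9.1 / 7.2 with no missing data: about half of the lost precision is recovered.

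**5. What the model cannot do.** For step 3's patients (20% stop, half of those lack week 14), a large-sample check of a missing-at-random model using weeks 2, 6 and 10 left a bias of 6.4-6.6 points when the missing patients gave no LDL-c after stopping. It fell to about 1-2 points only when they had off-drug values at week 6 or 10.

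**The case against.** The strongest reply is that the plan protects intention-to-treat through follow-up. Several sections keep patients who stop drug in the study to its end, and section 9.5 counts safety stops in the analysis. This stands. A reader might infer that everyone who stops drug is excluded; the documents do not support that. An off-drug week-14 draw is planned data, and the gap is confined to patients who withdraw or miss that visit.

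Three further inferences also go too far.
- **The discontinuation panel fills the week-14 slot.** The shared schedule column lists procedures, and nothing says an early panel counts as week 14. The plan is silent, which calls for a rule but does not show carry-forward.
- **Week 6 LDL-c is never used.** Section 9.1 uses it in a dose-escalation rule, which differs from the rule in section 5.1; the two must be reconciled. The statement holds only for the analyses in section 9.6. Week 6 also precedes the planned titration, so it informs the week-14 estimate but does not measure the week-14 regimen.
- **A mixed model would remove a 6.5-point bias.** That figure assumes all discontinuers are on rosuvastatin, and a missing-at-random model leaves it almost untouched if the missing patients' earlier values were all on drug.

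It is also fair that most of the precision gain comes from baseline adjustment, that power at 40 enrolled stays above 90% with 8 values lost, and that a log-scale model changes the summary measure. None of this supplies a missing-data rule, justifies leaving out week-2 LDL-c, or makes logistic regression suitable.

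**Conclusion.** The point holds in this form: the named method leaves out any randomised patient without a week-14 LDL-c despite its label, does not adjust for week-2 LDL-c or the stratification factors, makes no use of weeks 6 and 10, and is stated alongside a regression that does not fit the outcome. The exclusion follows from the method and the absence of a rule; the plan does not state it outright.

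The firmest part of the gain is baseline adjustment. The 15-47% variance reduction rests on assumed correlations and equal variances on the mg/dl scale, and the 2-11% from weeks 6 and 10 arises only with 10-27% missing. The bias cannot be predicted from the documents; the 1-2 mg/dl, 3-point and 6.5-point figures each rest on an assumed pattern of missingness, and the last is a one-arm extreme. The model removes bias only where earlier LDL-c values predict the missing ones. This should be changed before analysis, but it does not put the trial's conclusions in doubt by itself.

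**What to change.** Replace the method in section 9.6.1 as follows.

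1. Define the intention-to-treat set as all randomised patients.
2. Make the primary analysis a repeated-measures model of LDL-c at weeks 6, 10 and 14, with week-2 LDL-c, arm, visit, arm-by-visit and the stratification factors. The week-14 arm contrast is the primary result. Reconcile the factors listed in sections 4.3.2 and 9.3 first.
3. Choose the scale in advance: percent change, which keeps the stated endpoint, or log LDL-c, stating that the result is then a percent difference in geometric means.
4. Count only an actual week-14 draw as week 14, on or off drug, and enter discontinuation-visit panels at their actual time.
5. Keep the t-test as a sensitivity analysis. Add one for data not missing at random, for example with missing discontinuers assumed to return to off-drug LDL-c.
6. Delete the logistic regression wording.

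The cost is revised SAP text and slightly more analysis work, with no new visits or samples. The primary result would rest on a missing-at-random assumption, which is why step 5 is needed; the log scale would also change the summary measure.

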4.3.2 Randomization

Subjects who meet enrollment criteria will be randomized at Week 2 (the end of the pravastatin 40ml daily run-in period) in a 1:1 ratio according to the study treatment that has been randomly assigned to the Patient Number on the Randomization List held by the local site pharmacist.

Randomization will be stratified by type of ART: patients taking any booster (ritonavir or cobicistat) as part of their ART regimen and patients not taking a booster.

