9.0 STATISTICAL CONSIDERATIONS

9.1 General Design Issues

HILLCLIMBER is a randomized, controlled, open-label phase II trial. 40 subjects not already on high dose statin therapy who have CHD and/or calculated 10-year ASCVD risk >15% will be included and started on moderate dose statin therapy (pravastatin 40mg daily) for an initial two-week run-in period. Subjects not demonstrating significant toxicity at week 2 will then be randomized to high intensity statin therapy (rosuvastatin 20mg) versus continuing moderate intensity statin therapy (pravastatin 40mg daily). At week 6, subjects in the rosuvastatin arm who do not demonstrate significant toxicity and whose LDL-c is >60mg/dl and decreased by less than 25% compared with week 2 will then have doses increased to rosuvastatin 40mg (high dose group). Efficacy and safety will be evaluated at Week 14.

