9.2.2 Secondary Endpoints

Secondary endpoints include mean percent changes in the following from week 2 to week 14:

- Lipid parameters (HDL-c, triglycerides, and total cholesterol),
- Inflammatory biomarkers (soluble CD163, ST2, high sensitivity troponin I, high-sensitivity CRP, PAI-1, Lp-PLA2)
- Viral and immunologic markers derived from PBMCs (such as T cell reactivity and viral reservoir persistence).
- Statin drug levels >400% expected steady-state dose level
- Hemoglobin A1c level

An additional secondary endpoint will evaluate safety, as measured by treatment-

emergent clinical and laboratory adverse events, of high versus moderate intensity statin therapy in HIV-infected persons taking ART who have coronary heart disease (CHD) and/or 15% or greater risk for ASCVD.

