9.4 Sample size and Accrual

The predicted percent reduction in LDL-c by rosuvastatin dose is as follows: 20mg (55-60%), and 40mg (60-63%). The predicted percent reduction in LDL-c by pravastatin 40mg is 30%. The expected difference in LDL-c for subjects receiving high (rosuvastatin 20-40mg daily) versus moderate (pravastatin 40mg daily) intensity statin doses in this study is therefore approximately 25-30% compared with moderate. In a landmark study of patients with CHD comparing high intensity statin (atorvastatin 80mg, which is similar in intensity of expected lipid lowering to rosuvastatin 20-40mg) versus pravastatin 40mg, mean LDL cholesterol levels during treatment were 62mg/dl and 95mg/dl for high intensity and pravastatin groups (with standard deviations of approximately 20mg/dl), respectively.

Given potentially lower baseline LDL cholesterol levels in this study (we expect mean LDL of participants will be approximately 105, including patients off statin therapy and those on low intensity therapy), realistic expected mean LDL cholesterol levels are 75mg/dl for the pravastatin group and 50mg/dl for the high-intensity/rosuvastatin group. These expected LDL cholesterol levels are similar to those seen in the high intensity versus lower intensity treatment groups in a more recent trial of lipid-lowering strategies in high-risk patients, in which there was no excess of adverse events in the higher-intensity group which achieved a mean LDL of 53.7mg. In order to have a power of 0.80 with a two-sided alpha of 0.05 to detect a 25mg/dl difference in LDL-c lowering with a standard deviation of LDL-c of 20, the desired sample size would be at least 11 cases and 11 controls. Given the potential for study drug discontinuation in an expected 8 or fewer patients (based on on-treatment symptoms being present in 5-20% of patients on statins), the goal subject enrollment for this study is 30 with a possible enrollment of up to 50 participants in order to ensure adequate power.

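### Section 9.6.1 names logistic regression as well as t-tests for a continuous primary endpoint with no responder definition; separately, 4.3.2 and 9.3 list different strata

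*Combined protocol and SAP*

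**What the plan says.** **Endpoint.** Section 9.2.1: "The primary efficacy endpoint is mean percent change in fasting LDL-c (mg/dl) from week 2 (end of run-in period) to week 14". The arms are to be compared on that mean. The secondary lipid endpoints have the same form: "Secondary endpoints include mean percent changes in the following from week 2 to week 14".

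**Analysis.** Section 9.6.1, headed as the primary analysis, has two paragraphs. The first applies intention to treat to the primary endpoint and plans "logistic regressions to compare percent change in LDL-c from week 2 to week 14". The second begins "The primary analysis will evaluate percent changes in LDL-c at week 14 compared with week 2" and ends by naming the method: "Two-sample t-tests will be performed using STATA version 14". Nothing says how the two methods relate. No binary outcome and no covariates are given for the logistic model.

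**Sample size.** Section 9.4 sizes the trial "to detect a 25mg/dl difference in LDL-c lowering with a standard deviation of LDL-c of 20", at power 0.80 and two-sided alpha 0.05, and arrives at 11 per arm.

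**Strata.** Section 4.3.2 gives one factor: "Randomization will be stratified by type of ART: patients taking any booster (ritonavir or cobicistat"), against those not taking one. Section 9.3 describes the same pharmacist-held list but adds known CHD as a second factor.

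**The concern.** Logistic regression needs a categorical outcome, and percent change in LDL-c is continuous. To apply it, someone must either choose a responder cut-point or turn the model round and regress arm on percent change. The plan specifies neither. Both yield an odds ratio, not the difference in mean percent change that section 9.2.1 asks for.

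The two paragraphs of 9.6.1 therefore attach two different methods to one primary endpoint. In an open-label trial, fixing the method in advance is a main protection against choosing it after week-14 LDL-c is known. If method or cut-point stays open, the most favourable result can be reported, and the false-positive rate can exceed 5%.

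The strata discrepancy is a separate and smaller matter. A reader cannot tell whether CHD was balanced by design, in a trial that admits patients both with CHD and with high risk alone.

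**Working it through.** **1. Is a responder defined anywhere?** Sections 9.2.1 and 9.2.2 give lipid endpoints as mean percent changes. The only percent threshold for LDL-c is in section 9.1: "LDL-c is >60mg/dl and decreased by less than 25% compared with week 2". That is a week-6 dose-escalation condition, not an endpoint. So there is no responder definition.

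**2. Which method does the sample size fit?** Inputs from section 9.4: difference 25 mg/dl, SD 20 mg/dl, two-sided alpha 0.05, power 0.80.

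- Normal approximation: n per arm = 2 × (1.960 + 0.842)² × (20/25)² = 2 × 7.85 × 0.64 = 10.05, rounded up to 11. The plan's figure is reproduced.
- Exact t-test: 11.09 per arm are needed; power at 11 per arm is 0.796.
- The same data dichotomised (assumption: normal changes, pravastatin mean change 0, cut midway at −12.5 mg/dl): responder rates are Φ(−12.5/20) = 0.266 and Φ(12.5/20) = 0.734. Then n per arm = [1.960 × √(2 × 0.5 × 0.5) + 0.842 × √(0.266 × 0.734 + 0.734 × 0.266)]² / 0.468² = 1.912² / 0.219 = 16.7, rounded up to 17. Power at 11 per arm is about 0.60.

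The stated 11 per arm belongs to a comparison of means. (It is in mg/dl while the endpoint is percent change; that is a different point.)

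**3. What could an open choice do to type I error?** The documents give no cut-points and no correlation between week-2 and week-14 LDL-c, so all of the following is assumed: lognormal LDL-c, SD 20; week-2 mean 75; both arms at 75 at week 14 under the null; cut-points of 25%, 30% and 40% reduction; correlation 0.3; 15 per arm (half the goal of 30 in section 9.4). Rejection rate if the best of the three cut-points or the t-test is reported:

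| Test used for the responder comparison | Best of three or t-test |
|---|---|
| Likelihood ratio | 0.167 |
| Fisher's exact | 0.063 |
| Wald | 0.052 |

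The t-test alone rejects in 0.047. Across 11, 15 and 20 per arm, correlations from 0.3 to 0.7, and a second null with both arms at 62.5, the ranges are 8–18% (likelihood ratio), 5–8% (Fisher) and 4.5–10% (Wald, with non-estimable fits counted as non-significant). The plan names none of these tests. Part of the likelihood-ratio excess is that test's own small-sample error: in the 15-per-arm setting above, one pre-chosen cut-point rejects in 0.03 to 0.08 of null trials.

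**4. Does the cut-point matter under the alternative?** With 75 vs 50 mg/dl at week 14, 15 per arm and correlation 0.3, likelihood-ratio power at cut-points of 25/30/40/50/60% is 0.79/0.81/0.79/0.70/0.25, against 0.86–0.87 for the t-test. The cut-points of 25%, 30% and 40% disagree with one another on significance in 26% of trials. The choice is not neutral.

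**5. Arm as outcome.** This model needs no cut-point. Under the same assumptions at correlation 0.3, with a likelihood-ratio test, it disagrees with the t-test in 1–2% of null trials and 1–4% under 75 vs 50. Taking the better of the two rejects in 6–7% of null trials, against 5–6% for the t-test in the same runs.

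**6. What would adjustment for week-2 LDL-c gain?** Power of the t-test, then of the adjusted linear model, under 75 vs 50:

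| Per arm | Correlation 0.3 | 0.5 | 0.7 |
|---|---|---|---|
| 11 | 0.74, 0.80 | 0.87, 0.89 | 0.973, 0.969 |
| 15 | 0.86, 0.91 | 0.95, 0.96 | 0.996, 0.996 |
| 20 | 0.94, 0.97 | 0.99, 0.99 | 1.00, 1.00 |

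The gain is 3 to 6 points at correlation 0.3 and about nil at 0.7, where the loss at 11 per arm is 0.973 − 0.969 = 0.004.

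**7. Strata.** Booster alone gives 2 cells; booster by known CHD gives 2 × 2 = 4. One list cannot have both structures.

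**The case against.** The strongest reply is that the method is already identifiable. Section 9.2.1 compares means, the paragraph of 9.6.1 that describes the primary analysis names t-tests, and section 9.4 sizes a two-mean comparison. Only one clause conflicts, and it may be a slip for linear regression. Most of this stands: the t-test is valid, can be run as written and is probably intended. But the conflicting clause sits under the same heading and refers to the primary endpoint, nothing ranks the two methods, and the documents do not say it is a slip.

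A reader might infer that the logistic analysis cannot be run at all. That goes too far, because a model with arm as outcome runs without a cut-point and nearly always agrees with the t-test (step 5). What remains is that it does not estimate the stated difference in means.

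A reader might also infer that the plan carries a type I error of 14% to 17%. The documents do not support this. No responder analysis is planned, the cut-points and correlation are assumed, and errors of that size arise only with the likelihood-ratio test.

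Finally, it is fair to say that the strata mismatch is unrelated to the choice of test. No planned analysis uses the strata, so it is no flaw in the t-test.

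**Conclusion.** The point holds as a wording conflict that should be fixed. Section 9.6.1 assigns a logistic model to a continuous endpoint, defines no responder, and names a second, suitable method without saying which governs. The trial does not lack a valid primary analysis.

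The textual conflict needs no simulation. The size of the consequence does, and it is uncertain: in the 15-per-arm, correlation-0.3 setting, selective reporting gives false-positive rates from about 5% to 17% depending on the test, under assumed cut-points and distributions. No single figure should be quoted as the error rate of this plan.

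Leaving out week-2 LDL-c costs some efficiency if the correlation is low; it does not bias the t-test and is not part of the defect. The strata discrepancy is real but minor: it concerns how the randomisation is described.

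**What to change.** **Required in 9.6.1:** delete the reference to logistic regression and name one primary method for the continuous percent change.

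Preferred wording: *Percent change in fasting LDL-c between week 2 and week 14 will be compared by intention to treat, using linear regression on randomised group, week-2 LDL-c and the stratification factors used in the randomisation list. The adjusted difference will be reported with its 95% confidence interval. A two-sample t-test will be a sensitivity analysis.*

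Keeping the two-sample t-test as the single primary method is acceptable. If a responder analysis is wanted, list it as secondary and fix its cut-point before week-14 LDL-c is analysed.

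**Separately:** check the pharmacist-held randomisation list and make 4.3.2 and 9.3 both state the strata it actually contains.

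**Cost:** a few lines of text and one check of an existing list. The endpoint and data collection do not change. The preferred model's only statistical cost is the loss of under 1 power point at high correlation shown in step 6.

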9.3 Randomization and Stratification

Subjects who meet enrollment criteria will be randomized at Week 2 in a 1:1 ratio according to the study treatment that has been randomly assigned to the Patient Number on the Randomization List held by the local site pharmacist. Randomization will be stratified by: (1) type of ART: patients taking any booster (ritonavir or cobicistat) as part of their ART regimen and patients not taking a booster; and (2) known CHD or not.

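### Randomisation is stratified, but no primary analysis method uses the strata; if the strata are prognostic, the planned t-test is conservative and its interval wider than needed

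*Combined protocol and SAP*

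**What the plan says.** Section 9.3 states "Randomization will be stratified by: (1) type of ART", meaning a ritonavir or cobicistat booster or none, "and (2) known CHD or not". Section 4.3.2 states "Randomization will be stratified by type of ART" and gives no second factor. Neither section mentions blocking or a block size.

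Section 9.2.1 defines the primary efficacy endpoint as mean percent change in fasting LDL-c from week 2 to week 14. Section 9.6.1 gives two methods for comparing the arms on it: logistic regressions, then "Two-sample t-tests will be performed using STATA version 14". No covariate or stratum is named for either, and no adjusted or stratified analysis appears elsewhere in section 9.

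Section 9.4 sizes the trial "In order to have a power of 0.80 with a two-sided alpha of 0.05" and "to detect a 25mg/dl difference in LDL-c lowering with a standard deviation of LDL-c of 20", and concludes that "the desired sample size would be at least 11 cases and 11 controls".

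**The concern.** Stratified, blocked allocation makes the arms nearly equal on the strata, which takes between-stratum variation out of the true sampling variance of the arm difference. A two-sample t-test does not know this and leaves that variation in its estimated standard error. If the strata are prognostic, the stated standard error is too large, the interval over-covers and the test rejects a true null less than 5% of the time.

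What is at stake is precision. Section 2.0 calls this a pilot for later, adequately powered studies, so the effect estimate and its interval are a main product. Section 9.6.1 also leaves the primary method ambiguous, because logistic regression does not fit a continuous percent change.

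**Working it through.** **Inputs from the documents.** Two-sided alpha 0.05, power 0.80, difference 25 mg/dl, SD 20 mg/dl, 11 per arm (section 9.4); allocation 1:1 (section 9.3). Sample sizes: 22 evaluable; 30 (22 plus the 8 discontinuations allowed for in 9.4); and 40 (sections 3.0 and 9.1).

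**Assumptions, because the documents are silent.** R², the share of outcome variance explained by the strata: 0, 0.1, 0.2, 0.3. Permuted blocks of 4 within four strata, each factor split 50/50. The mg/dl inputs stand in for the percent scale, whose SD is not given.

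**Step 1: the plan's own figure.** n per arm = 2 × (1.960 + 0.842)² × (20/25)² = 10.05, rounded up to 11. This reproduces the plan. Power at 11 per arm is 0.834 by the normal formula and 0.796 by the noncentral t; 12 per arm gives 0.833 by the noncentral t.

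**Step 2: the mechanism in closed form.** With near-perfect balance on the strata, the true standard error is about √(1−R²) times the one the t-test reports. The t-test then rejects a true null with probability of about P(|t| > t₀.₉₇₅ / √(1−R²)). At N=30 (28 df, critical value 2.048):

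- R² = 0.1: threshold 2.159, type I error 0.040
- R² = 0.2: threshold 2.290, type I error 0.030
- R² = 0.3: threshold 2.448, type I error 0.021

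The adjusted interval has 26 df (critical value 2.056), so its relative width is 2.056 × √(1−R²) / 2.048. That is 4.8%, 10.2% and 16.0% narrower.

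**Step 3: simulation.** The t-test was compared with a linear model on arm plus two stratum main effects (8,000 null and 4,000 alternative trials per setting). Effect 25 mg/dl, SD 20, that is 1.25 SD.

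| N | R² | Type I error, t-test | Type I error, adjusted | Mean 95% half-width under the null, t-test → adjusted (mg/dl) | Power, t-test → adjusted |
|---|---|---|---|---|---|
| 22 | 0 | 0.048 | 0.050 | 17.58 → 17.84 | 0.793 → 0.779 |
| 22 | 0.1 | 0.036 | 0.045 | 17.60 → 16.91 | 0.802 → 0.820 |
| 22 | 0.2 | 0.033 | 0.053 | 17.69 → 15.98 | 0.799 → 0.855 |
| 22 | 0.3 | 0.025 | 0.050 | 17.77 → 14.98 | 0.816 → 0.908 |
| 30 | 0 | 0.049 | 0.049 | 14.85 → 14.96 | 0.914 → 0.911 |
| 30 | 0.1 | 0.041 | 0.052 | 14.91 → 14.22 | 0.911 → 0.924 |
| 30 | 0.2 | 0.028 | 0.047 | 14.95 → 13.41 | 0.927 → 0.956 |
| 30 | 0.3 | 0.021 | 0.046 | 14.91 → 12.50 | 0.946 → 0.979 |
| 40 | 0 | 0.051 | 0.048 | 12.71 → 12.75 | 0.967 → 0.967 |
| 40 | 0.1 | 0.043 | 0.052 | 12.74 → 12.12 | 0.974 → 0.981 |
| 40 | 0.2 | 0.032 | 0.052 | 12.74 → 11.40 | 0.983 → 0.991 |
| 40 | 0.3 | 0.020 | 0.046 | 12.78 → 10.72 | 0.985 → 0.995 |

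Monte Carlo error on a 0.05 rate is about √(0.05 × 0.95 / 8000) = 0.0024. Repeating N=30 with 40% on a booster and 50% with CHD gave the same type I error pattern and narrowing, with power gains of up to about 4 points. At R² = 0 the adjusted interval is wider by about 1.5% (N=22), 0.7% to 0.8% (N=30) and 0.3% to 0.4% (N=40).

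**Step 4: no blocking.** If the list is not blocked within strata, the t-test's type I error at N=30 stays at about 0.045 to 0.055 for R² of 0 to 0.2. Adjustment at R² = 0 then widens the interval by about 4%.

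**The case against.** The strongest objection is that nothing in the documents shows the strata to be prognostic. Their discussion of boosted regimens concerns drug interactions and safety (section 2.1). Section 2.1 describes rosuvastatin's interaction with protease inhibitors as negligible, and two boosted regimens are excluded (section 4.2.3). Nothing says that CHD predicts percent change in LDL-c, and the endpoint is measured from a value taken on a common run-in statin. R² could be near zero; at R² = 0.05 and N=30 the interval narrows by only about 2%. This stands, and it is why the loss can be stated only conditionally.

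The second objection is that planned power is not in danger. At 1.25 SD the t-test already has about 0.91 power at N=30 and 0.97 at N=40. That also stands on the plan's inputs, although those are in mg/dl and the endpoint is a percent. The effect on type I error and interval width does not depend on the assumed effect size.

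Three stronger readings do not hold:

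- A reader might infer that the loss is certain. It requires both prognostic strata and blocked allocation, and the documents establish neither.
- A reader might infer that the balance from stratification is wasted. The point estimate keeps it: under blocked stratification the t-test's simulated power at N=30 rises from 0.911 to 0.946 as R² goes from 0.1 to 0.3.
- A reader might infer that the t-test is biased or produces false positives. Its error is in the conservative direction.

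**Conclusion.** The gap is real: the strata in sections 9.3 and 4.3.2 are not used by any method in section 9.6.1. Its consequence is conditional and modest. Under blocks of 4 and assumed R² of 0.1 to 0.3 at N=30, type I error is about 0.04 to 0.02 instead of 0.05, and adjustment narrows the interval by about 5% to 16%. On 25 mg/dl and SD 20 the power gain is about 1 to 4 points at N=30, 1 or less at N=40, and 2 to 9 if only 22 are evaluable. With non-prognostic strata there is no gain and a cost of about 0.4% to 1.5% in interval width.

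The conclusion rests on R², the strata proportions and the block size, none of which the documents give. It is a free improvement of minor to moderate weight, concerning precision and coverage and not validity.

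**What to change.** In section 9.6.1, replace both the logistic-regression wording and the t-test wording with one primary model: a linear regression of percent change in LDL-c from week 2 to week 14 on treatment arm plus main effects for the stratification factors actually used on the randomisation list. Changing only the t-test sentence would leave two conflicting primary methods. Use main effects, not all four cells, so that sparse cells do no harm. Report the adjusted mean difference with its 95% interval as the primary result, and keep the t-test as a supporting analysis.

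Reconcile section 4.3.2 with 9.3 against the list held by the pharmacist, so that the model terms are fixed in advance, and state there whether allocation is blocked within strata.

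The cost is a short edit to 9.6.1, one consistency correction and one regression command. No new data are needed: the current ART regimen and CHD history are already collected (sections 6.3.2 and 6.3.3). Statistically it costs one or two degrees of freedom, about 0.7% of interval width at N=30 under blocking if the strata are not prognostic, or about 4% if the list is not blocked.
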